### 3 INTRODUCTION

## 3.1 Idiopathic Pulmonary Fibrosis

Idiopathic pulmonary fibrosis (IPF) is a chronic, progressive, and fatal lung disease of unknown cause that is characterized by worsening dyspnea, cough, and progressive loss of lung function due to scar formation in the lung. IPF belongs to a family of lung disorders known as interstitial lung diseases (ILDs) and is characterized by the pathological and radiographic pattern known as usual interstitial pneumonia (UIP). A diagnosis of IPF is diagnosis of exclusion, as it is reserved to those individuals with the UIP pattern of lung injury without any identifiable cause such as connective tissue disease or environmental exposure. It is a progressive disease in which scarring and lack of elasticity in the lung continues to increase until the majority of patients die from respiratory failure. Non-drug treatments include supplemental oxygen, pulmonary rehabilitation, and lung transplant.

To date, 2 drugs have been approved for treatment of IPF in several countries globally: pirfenidone, a small-molecule inhibitor of fibrosis (precise mechanism of action is unknown), and nintedanib, a triple tyrosine kinase inhibitor, that blocks signaling from vascular endothelial growth factor, fibroblast growth factor-, and platelet-derived growth factor receptors. In separate Phase 3 trials in IPF patients, both pirfenidone and nintedanib slowed the rate of decline in forced vital capacity (FVC). In addition, nintedanib significantly improved respiratory related quality of life. Both drugs have significant gastrointestinal side effects, many patients progress despite treatment and as such, there remains a significant unmet need based on the benefits and risks of the approved treatments.

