# 7.2 Method of Treatment Assignment

Blinded treatment assignments will be managed using interactive response technology (IRT). Each cohort will be randomized to treatments independently in the IRT.

Before the study is initiated, users at each investigative site will receive log-in information and directions on how to access the IRT system. At the time of the screening visit, immediately after informed consent is obtained and before any study-related procedures are performed, the investigative site will access the IRT system for assignment of a participant number for all participants, including participants not subsequently randomized or treated. The participant number is assigned sequentially by the system and will be unique across all sites. The participant number will not be used for any other participant. If a participant is rescreened, they will be given a new participant number.

Prior to the dosing on Day 1, participants who meet all criteria for enrollment at screening and Day 1 will be centrally randomized in a 1:1:1 ratio to BMS-986278 30 mg BID, BMS-986278 60 mg BID, or placebo, determined by a computer-generated randomization schedule using the IRT. The randomization lists will be generated by the IRT vendor using a permuted block design within each combination of stratum level. For the IPF cohort, randomization will be stratified by country (non-Japan versus Japan). Participants will be further stratified according to concomitant use of approved IPF therapy (pirfenidone vs nintedanib vs none). For the PF-ILD cohort, randomization will be stratified by UIP pattern (present vs absent) of lung injury on either

Protocol Amendment No.: 05

centrally-read HRCT, surgical lung biopsy, or cryobiopsy. Approximately 75 of 120 participants (62.5%) are expected to have UIP pattern of lung injury. Stratification for the PF-ILD cohort will also be based on category of background therapy (immunosuppression alone [ie, azathioprine, mycophenolate mofetil, mycophenolic acid, and/or tacrolimus] versus anti-fibrotic [nintedanib, pirfenidone] versus none).

After randomization, a medication kit/container number will be assigned to the participant corresponding to the treatment assignment. At subsequent visits, when new treatment containers need to be provided, the investigative site will access the IRT to obtain the container number assigned to the participant.

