## 10.4.1 Efficacy Analyses

## 10.4.1.1 Primary Efficacy Endpoint

The primary endpoint is the rate of change in ppFVC in IPF participants (estimated from measurements taken over 26 weeks of treatment). The decrease in ppFVC is assumed to be linear within each participant over the 26 weeks.

The primary analysis will compare the rate of change in ppFVC from baseline to Week 26 using a random coefficient linear mixed model using the Full Analysis Set (FAS). The model will include ppFVC at each visit as dependent variable, random coefficients for intercept and slope and fixed effect terms for treatment, time since randomization, treatment × time interaction, and baseline stratification factors. No imputation of missing values will be performed for the primary analysis. Sensitivity analysis may be performed to assess the impact of missing values as well as impact of dose reduction on the primary analysis. There will be no adjustment for multiple comparisons.

Subgroup analyses will be performed for concomitant use of pirfenidone or nintedanib therapy (vs neither pirfenidone nor nintedanib) for IPF and for other demographic and baseline characteristics.

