## 10.4.1.2 Secondary Efficacy Endpoints

All secondary analyses will be based on the FAS population. As appropriate, continuous secondary endpoints will be analyzed using mixed model repeated measures (MMRM) with a random effect for participant and fixed effects for treatment, visit, treatment-by-visit interaction, and baseline stratification factors. The baseline value of the endpoint being tested will be added into the model as a covariate. In addition, as appropriate analysis of covariance models will be used to analyze continuous secondary endpoints with treatment and factors used for randomization as fixed effects. The baseline value will be added into the model as a covariate.

Cochran-Mantel-Haenszel tests will be used to compare dichotomous endpoints between either BMS-986278 dose group vs placebo.

The Kaplan-Meier product limit method will be used to estimate the survival curves for time-to-event endpoints. Treatment comparisons between each BMS-986278 dose group and placebo will be performed using the log-rank test stratified by baseline stratification factors.

The PF-ILD cohort will be analyzed separately from the primary study cohort of IPF. The PF-ILD statistical analysis methods will be similar to IPF cohort. The details will be described in the SAP.

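### The primary slope model adjusts the level of ppFVC, but not its slope, for the stratification factors, so its confidence interval may be slightly conservative

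*Combined protocol and SAP*

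**What the plan says.** Section 10.4.1.1 specifies a random-coefficient linear mixed model for ppFVC at each visit, with "random coefficients for intercept and slope and fixed effect terms for treatment, time since randomization", followed by "treatment × time interaction, and baseline stratification factors". The quantity of interest is a slope: "The decrease in ppFVC is assumed to be linear within each participant over the 26 weeks". No interaction of a stratification factor with time is listed.

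Section 7.2 says the randomisation lists are built "using a permuted block design within each combination of stratum level". For IPF the factors are country (Japan or not) and background antifibrotic (pirfenidone, nintedanib or none). For PF-ILD they are UIP pattern and category of background therapy.

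On whether strata might differ in slope, section 3.1 says of separate Phase 3 trials in IPF that "both pirfenidone and nintedanib slowed the rate of decline in forced vital capacity (FVC"). For PF-ILD, section 10.4.1.2 says: "The PF-ILD statistical analysis methods will be similar to IPF cohort".

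**The concern.** A main effect for a stratification factor moves a participant's whole ppFVC line up or down. It does not change the line's steepness, which is what the treatment × time term compares. The strata are thus in the primary model but do almost nothing for the primary contrast.

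If participants on an antifibrotic decline more slowly than those on none, that difference stays in the random-slope variance. Stratified blocks have already balanced it across arms, so the estimate varies less than its reported standard error says. The secondary analyses in section 10.4.1.2 do not share this feature: in the ANCOVA and the stratified log-rank test, the strata act directly on the quantity compared.

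Precision is at stake. Section 10.1 justifies the sample size by interval width, and at 80 per arm the lower bound in Table 10 is only 0.49.

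**Working it through.** **Inputs from section 10.1.** Difference 2.5 points of ppFVC, SD 6.5, 80 per arm, two-sided 0.05 per dose.

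**Assumed, because the documents do not give them.** Slope gap d between participants on and off background therapy, in points per 26 weeks, and the share p of participants on one side of that split. A gap of 2.5 equals the effect the trial calls meaningful and is 2.5/6.5 = 0.38 SD.

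**Step 1: the plan's own figure.** SE = 6.5 × √(2/80) = 1.028. Half-width = 1.96 × 1.028 = 2.014. Interval = 2.5 ± 2.014 = 0.49 to 4.51, as in Table 10. The rows for 60 (0.17 to 4.83) and 100 (0.70 to 4.30) also reproduce. Table 10 uses the unadjusted SD and takes no credit for stratum adjustment. Power at 2.5 is Φ(2.5/1.028 − 1.96) = 68.2%.

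**Step 2: do main effects adjust the slope contrast?** With complete data at common visits, the contrast reduces to the difference between arms in mean participant slope, which a shift in level does not touch. A small set of fitted mixed models (15 to 60 runs per setting; visits at weeks 0, 4, 8, 12, 16, 20 and 26; assumed residual SD 2.5 and intercept SD 12) agreed. With complete data, the estimates with and without main-effect strata were identical. With 20% dropout they differed by at most 0.025 points.

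**Step 3: what factor × time terms would gain, in closed form.** Share of slope variance explained: R² = p(1 − p)(d/6.5)². Adjusted half-width = 2.014 × √(1 − R²).

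| d | p | R² | Half-width | Narrower by |
|---|---|---|---|---|
| 0 | any | 0 | 2.014 | 0% |
| 1.25 | 1/2 | 0.9% | 2.005 | 0.5% |
| 2.5 | 1/2 | 3.7% | 1.977 | 1.9% |
| 2.5 | 2/3 | 3.3% | 1.981 | 1.7% |
| 5.0 | 1/2 | 14.8% | 1.859 | 7.7% |
| 5.0 | 2/3 | 13.1% | 1.877 | 6.8% |

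At d = 2.5 the lower bound in Table 10 would move from 0.49 to 0.52. A 5% narrower interval needs R² = 1 − 0.95² = 9.75%, so d = 6.5 × √(0.0975/[p(1 − p)]). That is 4.1 points at p = 1/2 and 4.3 at p = 1/3 or 2/3.

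**Step 4: simulation.** 240 participants, permuted blocks within country × therapy, 8,000 runs per row, analysis of participant slopes; assumed two-thirds on therapy and 15% Japan.

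| Slope gap | Width ratio | Coverage, main effects only | Power, main effects → with × time |
|---|---|---|---|
| 0 | 1.000 | 94.8% | 67.2% → 67.1% |
| 2.5, therapy | 0.984 | 95.5% | 68.7% → 70.0% |
| 2.5, therapy and country | 0.974 | 95.6% | 68.0% → 70.0% |
| 5.0, therapy | 0.932 | 96.6% | 68.4% → 73.5% |

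The mean estimate was within 0.02 of the true 2.5 in every row. The Monte Carlo standard error of a coverage near 95% is √(0.05 × 0.95/8000) = 0.24 points, so the first row is consistent with nominal coverage. The few mixed-model runs with dropout gave similar width ratios (0.978 at d = 2.5, 0.924 at d = 5).

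**Step 5: PF-ILD.** Take 40 per arm, UIP present in 62.5% (section 7.2), and assume SD 6.5, a one-third to two-thirds therapy split, independent factors and the same gap d for both. SE = 6.5 × √(2/40) = 1.453. R² = (0.625 × 0.375 + 1/3 × 2/3)(d/6.5)² = 0.4566 × (d/6.5)².

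- d = 2: R² = 4.3%, SE 1.422, interval 2% narrower.
- d = 4: R² = 17.3%, SE 1.322, interval 9% narrower.

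**The case against.** The strongest reply is that the loss is conditional and probably small. No section gives a slope by stratum or the IPF stratum proportions. Section 3.1 reports drug effects in separate trials, whereas the strata here are users and non-users by choice. Under section 6.1 the none stratum also admits past users who have been off drug for 4 weeks. Nothing in the documents suggests a slope difference by country. All of this stands, and it is why the size is given as a range starting at zero.

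Secondly, PF-ILD was not sized on statistical grounds (section 10.1), and its planned analysis is descriptive (section 10.4.4). Power and type I error carry little weight there. Interval width still does, since that analysis rests on effect sizes and intervals.

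Thirdly, section 10.4 presents itself as a summary and defers detail to an SAP whose model statement is not in the documents. The SAP may therefore name the terms. That does not remove the point: the model as stated omits them, and would give the conservative interval if followed.

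Finally, main-effect adjustment is a valid choice, and the extra terms gain nothing if slopes do not differ. Both are true. The case for the change is that it costs almost nothing.

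**Conclusion.** The structural point holds: as written, the primary slope contrast is essentially unadjusted for the strata used in randomisation. The consequence is a possible loss of efficiency that depends on unknown slope differences. For IPF the interval would narrow by 0% with no gap, about 2% at a 2.5-point gap and 7 to 8% at 5 points, given SD 6.5, 80 per arm and one-third to two-thirds on background therapy. The gain could be larger in PF-ILD if both factors predict slope.

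Three stronger readings are tempting and are not supported:

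- That the interval is certainly too wide. This needs slope differences by stratum, which the documents make plausible for antifibrotic use but do not show.
- That the primary test is biased or its error rate inflated. The estimate is unbiased, and any error is on the conservative side.
- That the sample size is wrong on this account. Table 10 assumes no stratum adjustment, so its stated precision does not depend on these terms.

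**What to change.** In section 10.4.1.1, keep the main effects and add stratification factor × time fixed effects:

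- IPF: country × time and background antifibrotic × time.
- PF-ILD: UIP pattern × time and background-therapy category × time, with the categories as randomised.

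Keep a single treatment × time contrast per dose, common to all strata. With additive terms no averaging over strata is needed, and no three-way interactions are proposed. Write the full model statement into the SAP before the first unblinding, which is when section 10.4 says the SAP will be final.

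The cost is three fixed-effect parameters per cohort: one for the two-level factor and two for the three-level factor. No new data or visits are needed. The downside is those few degrees of freedom, with no gain if slopes do not differ by stratum.

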Nintedanib and BMS-986278, in combination, was well tolerated in two range-finding studies. In one range-finding study, the observed decrease in nintedanib exposure was attributed to the vehicle. BMS-986278 doses selected for the definitive 3-month combination toxicology study in rat were 30/15 mg/kg/day (male/female) and dosing was initiated concurrently. No PK or toxicological interaction were noted between BMS-986278 and nintedanib.

In a definitive 3-month combination toxicology study, BMS-986278 doses in the pirfenidone combination part of the study were 15 mg/kg/day in males and 7.5 mg/kg/day females (1 to 3× projected high/low human efficacious AUC) and that of pirfenidone was 500 mg/kg/day (1× MRHD). There were no unique clinical pathology or anatomic pathology findings when BMS-986278 was administered in combination with pirfenidone at doses providing clinically relevant exposures. All findings were consistent with those reported previously for each drug alone.  There was a slight increase in alanine aminotransferase (ALT) levels in animals receiving the combination (1.41 to 1.45×). When administered in combination with pirfenidone, BMS-986278 systemic exposures (maximum concentration [Cmax] and AUC[0-24h]) were 0.2 to

Protocol Amendment No.: 05

0.5× those when administered alone, indicating a possible toxicokinetic interaction in rat. Although initiation of pirfenidone dosing 1 week ahead of BMS-986278 enabled development of tolerance to the central nervous system-related signs caused by pirfenidone, clinical signs were observed sporadically in a small number of rats after BMS-986278 administration was initiated on Day 8 in a small number of rats. Additionally, 4 rats were euthanized or found dead on or after Day 45 (3 in the combination group compared to 1 in the pirfenidone alone group). However, when accounting for the different group sizes, there was a similar incidence [5% to 8%] in the combination and pirfenidone-only treatment groups. Nevertheless, the clinical signs and mortality suggested a possible toxicologic interaction between BMS-986278 and pirfenidone.

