BMS-986278 doses in the nintedanib combination part of the study were 30 mg/kg/day in males and 15 mg/kg/day females and that of nintedanib was 20 mg/kg/day. There was no toxicokinetic or toxicologic interaction between BMS-986278 and nintedanib when coadministered at doses providing clinically relevant exposures. All findings were consistent with those reported previously for each drug alone.

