#### 5.1.2 Treatment Period

In the primary cohort of IPF participants, eligible participants will be randomized to receive 1 of 2 dose levels of BMS-986278 (30 mg or 60 mg BID) or placebo for 26 weeks. Randomization will be stratified by country (non-Japan versus Japan), and concomitant use of approved IPF therapy (pirfenidone versus nintedanib versus none).

In the secondary cohort of PF-ILD participants, eligible participants will be randomized to receive 1 of 2 dose levels of BMS-986278 (30 mg or 60 mg BID) or placebo for 26 weeks. Randomization will be stratified by UIP pattern (present vs absent) of lung injury and by category of background therapy (ILD-targeted immunosuppression [ie, azathioprine, mycophenolate mofetil, mycophenolic acid, and/or tacrolimus] alone versus anti-fibrotics [nintedanib, pirfenidone] with or without ILD-targeted immunosuppression versus no ILD-targeted immunosuppression or anti-fibrotics).

All participants randomized will undergo functional, quality-of-life, PK and biomarker assessments according to the Schedule of Activities (Table 1).

In addition, physical examinations, vital sign measurements (including orthostatic assessments), 12-lead ECGs, and clinical laboratory evaluations will be performed at selected times throughout the dosing interval. Participants will be closely monitored for AEs throughout the study.

For all study participants, blood samples will be collected for up to 4 hours after study treatment administration for PK analysis on Day 1. Predose blood samples will be collected at Week 12 and Week 26. Additional samples will be collected from IPF and PF-ILD participants in the intensive PK substudy (see Section 9.5.2).

After completing the 26-week main study, participants will have the opportunity to continue study treatment in the OTE for another 26 weeks. Refer to the assessments in the Schedule of Activities (Table 2) and Sections 7.1 and 7.2 for treatments administered and treatment assignments, respectively.

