# 2) Prior Therapy

- a) Use of systemic corticosteroids equivalent to prednisone > 15 mg/day within 2 weeks of Day 1. See Section 7.7.1 for guidance in the OTE.
- b) **Not applicable per Revised Protocol 03**. Use of azathioprine, cyclophosphamide, cyclosporine, methotrexate, leflunomide, mycophenolate mofetil, mycophenolic acid, and/or tacrolimus within 4 weeks of Day 1. Additionally, use of rituximab or other specific B-cell depleting therapies within 6 months of Day 1. Disease modifying anti-rheumatic drugs (DMARDs), including but not limited to hydroxychloroquine, sulfasalazine, anti-TNF alpha antagonists, interleukin antagonists, abatacept, tofacitinib, and baricitinib, will be permitted as long as these agents have been in place and stable for at least 6 months prior to screening (refer to Section 7.7.). See Section 7.7.1 for guidance in the OTE.
- c) Use of potent inhibitors of OATPs, defined as inhibitors expected to increase exposures of OATP substrates by more than 2× within 4 weeks of Day 1 (see APPENDIX 5).
- d) Use of potent inhibitors or inducers of cytochrome P450 CYP3A4 or CYP2C8 (see APPENDIX 6 and APPENDIX 7, respectively) within 4 weeks of Day 1.
- e) Received experimental IPF or other experimental ILD therapy within 4 weeks before screening.
- f) Not applicable per Protocol Amendment 04; refer to Exclusion Criterion 2)i. Longacting phosphodiesterase 5 inhibitors (eg, tadalafil, vardenafil). Daily use of short-acting phosphodiesterase 5 inhibitors (eg, sildenafil) taken as needed for erectile dysfunction is allowed during the study, but is not allowed within 7 days pre or post Day 1. Short-acting phosphodiesterase 5 inhibitors taken daily for treatment of pulmonary arterial hypertension are not allowed during the study.

Protocol Amendment No.: 05

g) Simultaneous use of pirfenidone and nintedanib at screening.

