## 7.7 Concomitant Therapy

For the PF-ILD cohort, mycophenolate mofetil, mycophenolic acid, azathioprine or and/or tacrolimus are permitted only if the participant is on a stable dose at least 6 months prior to screening. These immunosuppressive medications cannot be initiated during the course of the main study.

Although pirfenidone or nintedanib are allowed during the main study for both cohorts, they are not allowed in combination with one another during the main study.

Stable DMARDs used to manage synovitis in rheumatoid arthritis patients will be permitted, as long as these agents have been in place and stable for at least 6 months prior to screening. DMARDs include, but are not limited to, hydroxychloroquine, sulfasalazine, anti-TNF alpha antagonists, interleukin antagonists, abatacept, tofacitinib, and baricitinib.

During the OTE, modifications and initiation of DMARD use are allowed per clinician discretion or patient preference.

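### Should the IPF background-therapy subgroup keep pirfenidone and nintedanib apart, as the randomisation does?

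*Combined protocol and SAP*

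**What the plan says.** Section 10.4.1.1 names one background-therapy subgroup for the IPF cohort: "Subgroup analyses will be performed for concomitant use of pirfenidone or nintedanib therapy (vs neither pirfenidone nor nintedanib) for IPF". The natural reading is two levels, any antifibrotic against neither. The same sentence goes on to promise further subgroups by demographic and baseline features, without listing them. Section 10.4 describes the whole part as a summary and leaves the detailed specification to a SAP, to be finalised before the first unblinding. No separate SAP text is in the supplied document.

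The randomisation factor has three levels. Section 7.2: "Participants will be further stratified according to concomitant use of approved IPF therapy (pirfenidone vs nintedanib vs none". Section 5.1.2 has the same factor: "concomitant use of approved IPF therapy (pirfenidone versus nintedanib versus none". The levels do not overlap. Section 6.2 excludes "Simultaneous use of pirfenidone and nintedanib at screening", and section 7.7 says of the two drugs that "they are not allowed in combination with one another during the main study".

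Section 3.4.3.4 gives the development aim: to show the drug safe and effective in IPF either alone or together with approved treatment.

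**The concern.** The trial takes the trouble to randomise within three groups and then names a subgroup analysis that merges two of them. Merging hides any difference between the two drugs, and the protocol gives a reason to wonder about one. In the rat combination study (section 3.4.3.4), exposure to BMS-986278 with pirfenidone fell to between 0.2 and "0.5× those when administered alone, indicating a possible toxicokinetic interaction in rat". For nintedanib the same section reports: "There was no toxicokinetic or toxicologic interaction between BMS-986278 and nintedanib when coadministered at doses providing clinically relevant exposures".

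If lower exposure meant a weaker effect in pirfenidone users, the merged estimate would average a weak and a full effect, and the reader would see neither. No analysis named in the protocol gives the difference in ppFVC slope separately for users of each drug.

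**Working it through.** **1. Is anything contradicted or biased?** The two-level subgroup is the three-level factor with two levels joined. Every participant falls in exactly one cell of either version, and both are set before treatment. Randomisation remains stratified at three levels, and the primary model includes the baseline stratification factors. The choice of subgroup display changes neither the primary estimate nor its test.

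**2. Does the split fit its question?** The aim in section 3.4.3.4 is a contrast between use with and without approved therapy. That has two levels.

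**3. Where is the interaction question handled?** The motivating signal concerns exposure in rats.
- Table 3 has an exploratory objective on interactions of nintedanib or pirfenidone with BMS-986278, by population PK.
- Sections 9.5.1 and 9.5.2 collect plasma samples for the specific background drug.
- Section 10.4.2 commits to a population-PK analysis of the sparse and intensive samples, and to summaries of nintedanib and pirfenidone trough levels by visit.
- Only the exposure-response step is conditional (sections 9.5.2 and 10.4.4).

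**4. What could a by-drug table show?** Inputs from section 10.1: SD 6.5, meaningful difference 2.5, 80 per arm, 80% completion (0.80 × 80 = 64 per arm).

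The plan's own figures come first. Table 10 follows from 2.5 ± 1.96 × 6.5 × √(2/n):
- n = 60: 0.17 to 4.83
- n = 80: 0.49 to 4.51
- n = 100: 0.70 to 4.30

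All three match. The same normal approximation is used below in place of the random-slope model.

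The documents give no shares for background therapy, so these are assumed. The base case is equal thirds: 80/3 = 26.7 per arm at each level, and 53.3 per arm on either antifibrotic.

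- One drug, one dose against placebo: SE = 6.5 × √(2/26.7) = 1.78; half-width 1.96 × 1.78 = 3.49.
- Both drugs together: SE = 6.5 × √(2/53.3) = 1.26; half-width 2.47.
- Difference in effect between the drugs: SE = √2 × 1.78 = 2.52. For 80% power the true difference must be 2.80 × 2.52 = 7.05 points, nearly three times the 2.5 that the plan calls meaningful.

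Now take an extreme case, which is an assumption and not in the documents: effect 0 with pirfenidone, 2.5 with nintedanib or no antifibrotic.
- Merged split: 1.25 against 2.5; gap 1.25, SE √(1.26² + 1.78²) = 2.18, z = 0.57, power 9%.
- By drug: gap 2.5, SE 2.52, z = 0.99, power 17%. The pirfenidone interval excludes 2.5 with probability Φ(2.5/1.78 − 1.96) = 29%.

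Against that, let the effect be 2.5 in everyone. The chance that the two drug-specific estimates still differ by at least 2.5 points is 2 × [1 − Φ(2.5/2.52)] = 32%, or 16% in the one direction that would point at pirfenidone.

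Ranges over shares of equal thirds, 20/50/30 and 40/40/20 (pirfenidone/nintedanib/none), at 80 and 64 per arm:

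| Quantity | Equal thirds, 80 per arm | Range |
|---|---|---|
| Half-width, one drug | 3.49 | 2.85 to 5.04 |
| Half-width, both drugs | 2.47 | 2.25 to 2.76 |
| SE, between drugs | 2.52 | 2.30 to 3.04 |
| Power, merged split, extreme case | 9% | 6% to 9% |
| Power, between drugs, extreme case | 17% | 13% to 19% |
| Pirfenidone interval excludes 2.5, extreme case | 29% | 16% to 34% |
| Gap of 2.5 or more, uniform effect | 32% | 28% to 41% |

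**The case for a change.** The best case for the concern is cost. A by-drug table follows the randomised strata, needs no new data and leaves the sample size, alpha and primary model alone. Naming it before unblinding would also stop anyone choosing it after seeing results. The PK work measures concentrations and does not give ppFVC slope by background drug. In the extreme case at equal thirds the by-drug display doubles the visible gap, from 1.25 to 2.5 points.

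All of this is true, and a sponsor who wants the table may include it. It does not make the plan deficient, for three reasons.

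- Section 10.4.1.1 already permits further baseline subgroups, and without the SAP text nobody can say that the table is missing.
- The signal behind it is weak. It comes from rats and is called only possible. The same section finds no unique pathology and, for deaths, "when accounting for the different group sizes, there was a similar incidence [5% to 8%] in the combination and pirfenidone-only treatment groups". Section 3.4.4.4 describes a human pirfenidone study but gives no results. Even the size of the rat signal does not imply a lost effect throughout: at the 0.5× end, 60 mg would give roughly the exposure of 30 mg, a dose that section 5.5 expects to work. This comfort does not extend to the 0.2× end.
- The table would be hard to read. Section 10.1 does not expect the two doses to be told apart on FVC with 80 per arm, where the SE of a difference is 6.5 × √(2/80) = 1.03. The between-drug SE of 2.52 is about 2.4 times that.

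**Conclusion.** The concern does not hold. The named subgroup is coarser than the randomisation factor, but merging two strata to gain precision is an ordinary choice, and here it fits the aim of the programme. Following the plan as written gives a sound primary result and an interpretable subgroup. The drug-specific interaction question is taken up where it belongs, in the PK objectives.

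A by-drug display would raise power in an extreme case from about 9% to 17%. With a uniform effect it would show an equally large gap in about a third of trials. Whether to add it is a matter of taste for the SAP. These figures rest on the protocol's SD of 6.5, a normal approximation to the slope analysis, and assumed shares of background therapy. The conclusion is the same across the range of shares tried.
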